6.1.9. Assessments for Premature Discontinuation from Study

If a subject discontinues study dosing (for example, as a result of an AE), every attempt should be made to keep the subject in the study and continue to perform the required study-related follow-up and procedures (see Section [6.1.10](#), Criteria for Discontinuation of Study Treatment). If this is not possible or acceptable to the subject or investigator, the subject may be withdrawn from the study. If the subject is withdrawn from the study, the following Early Termination procedures should be performed if possible:

- Administer CFQ-R (prior to any procedures), SNOT-22 and TSQM
- Review of AEs and concomitant medications
- Complete physical examination including body weight
- Obtain vital signs
- Obtain serum pregnancy test (for females of child-bearing potential only)
- Obtain blood for PK, ADA analysis, and biomarkers
- Obtain blood and urine for safety lab
- Obtain oxygen saturation
- Obtain pre- and post-bronchodilator spirometry
- Obtain induced sputum

6.1.10. Criteria for Discontinuation of Study Treatment

Study medication may be discontinued in the following instances:

- Intercurrent illness that would, in the judgment of the investigator, affect assessments of clinical status to a significant degree. Following resolution of intercurrent illness and/or fever, and in collaboration with the medical monitor, the investigator may decide to allow the subject to resume study dosing.
- Unacceptable toxicity, or toxicity that, in the judgment of the investigator, compromises the ability to continue study-specific procedures or is considered to not be in the subject's best interest
- Subject request to discontinue for any reason
- Subject noncompliance
- Pregnancy during the study; refer to [Appendix 3](#)
- Discontinuation of the study at the request of Gilead, a regulatory agency or an IRB/IEC

6.2. End of Study

The end of this study is defined as the date of the last study visit of the last study subject.

6.3. Details of Scheduled Assessments

6.3.1. Physical Exam

A complete physical exam will be performed at Screening and the 30-day Follow-up Visit. A symptom-driven physical exam will be performed at Baseline, Weeks 4, 8, 12, 16, 20, and 24, and can be performed as needed at other study visits.

All physical exams will include a body weight measurement. Height will be captured at Screening only.

A musculoskeletal symptom assessment will be conducted at Screening, Baseline, and at Weeks 4, 8, 12, 16, 20, 24, and 30-day follow-up visit.

6.3.2. Vital Signs

Vital signs to be collected include resting blood pressure, pulse, respiratory rate and temperature.

6.3.3. CFQ-R, TSQM, and SNOT-22 Questionnaires

The CFQ-R is a CF-specific quality of life measure encompassing both generic and CF-specific domains for a 2-week recall period. Because all study subjects will be 18 years of age or older, only the self-administered version of the questionnaire will be used in this study.

The questionnaire takes approximately 15 minutes to complete and will be administered before any other study procedures at study visits indicated in [Table 6-1](#). This questionnaire will be in electronic form and accessed on a secure website using a PC or laptop computer, where available.

The TSQM questionnaire is a generic medication acceptance measure designed to assess effectiveness, side effects, convenience, and global satisfaction. It is self-administered questionnaire that takes approximately 15 minutes to complete and will be administered before any other study procedures at study visits indicated in [Table 6-1](#). This questionnaire will be in electronic form and accessed on a secure website using a PC or laptop computer.

The Sino-nasal Outcome Test (SNOT-22) is a symptom-based rhinosinusitis outcome measure. The questionnaire is self-administered with 22 questions that takes approximately 15 minutes to complete. It will be administered before any other study procedures at study visits as indicated in [Table 6-1](#). This questionnaire will be in paper form.

Questionnaires should be obtained prior to any other procedures. At visits where there are multiple questionnaires, the CFQR should be completed first, then SNOT-22 and then TSQM. If on a given visit SNOT-22 is not done then the CFQ-R is completed first and then the TSQM.

6.3.4. Pulmonary Exacerbation Evaluation

A modified version of the Fuchs criteria {[Ramsey et al 2011](#), [Wainwright et al 2015](#)} will be used for categorization of pulmonary exacerbations during the course of the study. A pulmonary exacerbation is defined as a change in antibiotic therapy (IV, inhaled, or oral) for any 4 or more of the following 12 signs/symptoms. New or changed antibiotic therapy from the previous visit for the following sinopulmonary signs/symptoms will be determined at all visits and documented in the source documents:

- Change in sputum
- New or increased hemoptysis
- Increased cough
- Increased dyspnea
- Malaise, fatigue, or lethargy
- Temperature above 38°C

- Anorexia or weight loss
- Sinus pain or tenderness
- Change in sinus discharge
- Change in physical examination of the chest
- Decrease in pulmonary function by 10 percent or more from a previously recorded value
- Radiographic changes indicative of pulmonary infection

6.3.5. Oxygen Saturation

Oxygen saturation by pulse oximetry will be performed as indicated in in [Table 6-1](#). Sites should follow their institutional guidelines for pulse oximetry. If a subject is on oxygen this should be measured after they have been off oxygen for at least 5 minutes.

6.3.6. Spirometry

All sites will be provided with centralized spirometry equipment to be used for spirometry assessments throughout the study. Spirometry data will be transmitted to a centralized spirometry vendor for quality review. In the Screening period, spirometry will be collected pre and post-bronchodilator, subjects are required to withhold their inhaled CF therapies including all bronchodilators. Two pre-bronchodilator spirometry measures are required using the study provided central spirometry equipment to meet the inclusion criteria. If a subject's Screening pre-bronchodilator FEV₁ % is 38-39.9% or 80.1-82% the upper limit FEV₁ % inclusion, baseline spirometry may be repeated one time assuming all other inclusion/exclusion criteria have been met. If a subject's relative change in FEV₁ % at Baseline from Screening is 12.1-14% the upper limit FEV₁ % inclusion, baseline spirometry may be repeated one time assuming all other inclusion/exclusion criteria have been met.

At all visits after Screening, including Baseline, spirometry should be performed at approximately the same time of the morning on designated study-specific days in [Table 6-1](#). ATS guidelines should be followed for all PFT maneuvers as well as for selecting specific PFT efforts to report {[American Thoracic Society Committee on Diagnostic Standards for Non-Tuberculous Respiratory Diseases 1995](#)}. Spirometry collected at Baseline and Week 8 visits will be reviewed for quality by the central spirometry vendor in real time to ensure that acceptable measurements are selected and to reduce variability at the Baseline visit. Additional study-specific PFT guidelines are outlined below.

Standard of care inhaled CF therapies (eg, bronchodilators, dornase alpha, inhaled antibiotics, hypertonic saline, inhaled corticosteroids) will be withheld prior to study specified spirometry in the treatment and follow-up period as follows:

Pre-bronchodilator spirometry is defined as occurring after a subject has:

- Withheld their short-acting beta-agonist (eg, albuterol/salbutamol) or anticholinergic (eg, ipratropium bromide) for more than 4 hours before the spirometry assessment; AND
- Withheld their long-acting bronchodilator (eg, salmeterol) for more than 12 hours before the spirometry assessment; AND
- Withheld their once-daily, long-acting bronchodilator for more than 24 hours before the spirometry assessment.

See [Appendix 5](#) for specific inhaled washout details.

Doses of bronchodilators taken within the previous 24 hours of spirometry will be recorded for each spirometry assessment.

Post-bronchodilator is defined according to ATS guidelines, occurring approximately 15 minutes after 4 puffs of a bronchodilator (ie, albuterol, salbuterol, or levalbuterol).

With the exception of the screening period, at all visits at which spirometry is indicated, both a pre-bronchodilator and a post-bronchodilator spirometry will be performed. In the event that a subject forgets to withhold their inhaled CF medications at Baseline or Week 8, the visit should be rescheduled to another date within the screening window. At all other visits, if a subject forgets to withhold their inhaled CF medications, spirometry should be performed post-bronchodilator only and recorded as such.

On days of study drug administration at the study site the post-bronchodilator FEV₁% predicted will be utilized as a safety measurement. If an individual subjects post-bronchodilator FEV₁% predicted is either 1) <40% predicted, 2) >30% below the Baseline FEV₁% predicted, or 3) PEF decreases by >30% from the mean obtained during Screening during non-spirometry visits, study drug dosing should be postponed and rescheduled during the study visit window.

Subjects should not be informed of their study-related spirometry results during the Blinded Treatment Period (Baseline through Week 8) regardless if the subject prematurely discontinues treatment. In addition, subjects should not be informed of their study drug allocation (active:placebo) until after all subjects have completed Part 1 of the protocol.

Refer to the Central Spirometry Study Manual for additional information about spirometry.

6.3.6.1. Real-Time Central Spirometry Over-Read

At Baseline and at Week 8, critical FEV₁ data points for the primary endpoint of the study, spirometry may be reviewed in real-time by the central spirometry reader. This real-time review should eliminate randomizing subjects that have unacceptable spirometry, exceed the FEV₁ reversibility inclusion criterion, or at Week 8 have unacceptable spirometry and may prevent unnecessary radiation exposure for subjects performing FRIs at these visits.

In the event that a real-time central spirometry over-read is not available at a given Baseline or Week 8 visit, the preferred option is to reschedule the subject for repeat spirometry (and FRI if applicable) within the study visit window. If this is not possible, the alternative will be to allow the study investigator to review the spirometry and if judged to be acceptable and meets the FEV₁ reversibility criterion for Baseline, the subject may proceed to Randomization or Week 8 Visit FRI (if applicable).

6.3.7. Peak Expiratory Flow Rate (PEFR)

PEFR measurements are a simple and useful objective measure to assess current lung function. At Screening subjects will be given a peak flow meter and be instructed in its proper use. Daily serial AM assessments prior to morning CF inhaled medications and inhaled bronchodilators will be captured during Screening to obtain a target of at least 7 days or more of data. A mean AM pre-bronchodilator PEFR will be calculated. PEFR should be taken around the same time each morning. The mean AM PEFR value calculated at Baseline will be utilized as an anchor to assess an individual subject's current lung function throughout the study.

On days of study drug administration that do not require study site spirometry (at study site or at subject's home) an AM pre-bronchodilator PEFR will be obtained. If the best of 3 PEFR measurements is >30% below the mean PEFR Baseline value, a subject may administer 2-4 puffs of a short-acting bronchodilator and repeat the PEFR 15-20 minutes later. If post-bronchodilator PEFR remains >30% below the mean PEFR value then dosing of study drug should be postponed and rescheduled within the study window.

Investigators may request subjects to perform additional unscheduled PEFR measurements throughout the study as judged by local clinical practice. These values should also be recorded.

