4.2. Inclusion Criteria

Subjects must meet all of the following inclusion criteria to be eligible for participation in this study.

- 1) Male or female 18 years of age or older
- 2) Confirmed diagnosis of CF as determined by the 2008 Cystic Fibrosis Foundation Consensus Report {[Farrell et al 2008](#)} criteria
- 3) Subjects must be able to perform acceptable and reproducible spirometry as per the American Thoracic Society (ATS) Guidelines
- 4) Must have a body weight of > 40 kg (88.2 lbs) at study Screening
- 5) Subjects must be a never-smoker or an ex-smoker with < 5 pack-year history of smoking and be smoke-free (including marijuana or e-cigarettes/vaping) for 12 months prior to Screening
- 6) Pre-bronchodilator $FEV_1 \geq 40\%$ and $\leq 80\%$ of predicted at Screening
- 7) Two pre-bronchodilator spirometry measures taken at least 4 days apart (one during Screening, one at Baseline) using the sponsor provided central spirometry equipment must meet the following 2 criteria:
 - The relative difference of $FEV_{1(L)}$, calculated as the absolute value of $[(\text{first } FEV_1 - \text{second } FEV_1) / \text{first } FEV_1] \times 100$ should be < 12% **AND**
 - The absolute difference in FEV_1 should be < 200 ml

8) Negative Investigation/History of Important Bacteria Infections:

Tuberculosis (TB):

— A negative QuantiFERON-TB Gold test during Screening

Non-Tuberculous Mycobacteria species (NTM):

— All sputum cultures for ANY *Mycobacterium spp.* performed 24 months prior to Screening must be negative. If only 1 NTM culture was performed 24 months prior to Screening, that NTM culture and the most recent NTM culture obtained >24 months prior to Visit 1 must both be negative **AND**

— A negative sputum culture \leq 12 months **prior to** Screening for any *Mycobacterium spp.* **AND**

— No current treatment for active NTM during Screening

Burkholderia spp.

— All sputum/throat cultures for ANY *Burkholderia spp.* performed 24 months prior to Screening must be negative. If only 1 *Burkholderia* culture was performed 24 months prior to Screening, that *Burkholderia spp.* culture and the most recent *Burkholderia spp.* culture obtained >24 months prior to Screening were both negative **AND**

— A negative culture for *Burkholderia spp.* during Screening **AND**

— No current treatment for *Burkholderia spp.* during Screening

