5.3. Dosage and Administration of GS-5745 and Placebo

GS-5745 or placebo for SC injection will be administered to subjects on the thighs, the stomach area (abdomen), or the deltoid area of the upper arms in the blinded phase of the study. In the OLE if self-injection at home is determined to be safe, deltoid injections will not be allowed. If the abdomen area is chosen, the area 5 cm (2 inches) around the umbilicus should be avoided. GS-5745 or placebo will be administered SC at the research center at study visits during the blinded phase of the study. If the dose requires multiple SC injections, all injections should be delivered within 1 hour. The investigator or a qualified designee must be present during the administration during the blinded phase of the study.

In the blinded phase of the study, if the subject has a body temperature of > 38°C (100.4°F), his/her FEV₁ % predicted is less than 40% or his/her FEV₁ % predicted decreases by > 30% from Baseline on study site visits requiring spirometry, AM pre-bronchodilator PEF decreases by >30% from the mean PEFR obtained during Screening during non-spirometry visits, or in the medical opinion of the investigator or home health provider the subject is unfit to receive study drug at a given visit, the subject should not be administered study drug. In consultation with the medical monitor, the Investigator may delay dosing until the parameters above are met. See Section 6.3.6 for additional information on the spirometry measures.

During the OLE portion of the study subjects will have the option to continue to receive study drug SC injections at their respective study clinic receive SC injections by a qualified home health provider (where available) at their residence in the short-term with the long-term plan to eventually self-administer the study drug without supervision at home after the DMC and Gilead have reviewed safety data and agree home administration appears safe. At the beginning of the

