OLE subjects will be instructed by clinic staff how to self-administer the SC injections using the thigh and stomach areas only. After successful training and sign-off by the study clinic and/or home health provider (where available) that the subject can correctly self-administered study drug, subjects will self-administer doses at home weekly (± 3 days) between study visits and record the doses when they are administered. Subjects who find it difficult to self-administer the study drug SC injections at home may receive assistance with the administration from the home health care service (where available) to ensure proper dosing and adherence or receive their SC injections at their local study sites. All injections should be delivered within 1 hour.

Subjects will also be instructed in the safe storage and transport of the study drugs as well as safe disposal of used syringes.

Similar to the blinded phase of the study, in OLE if the subject has a body temperature of $> 38^{\circ}\text{C}$ (100.4°F), PEF decreases by $> 30\%$ from the mean obtained during Screening during non-spirometry visits, or in the medical opinion of the investigator or home health provider the subject is unfit to receive study drug at a given visit, the subject should not be administered study drug. In consultation with the medical monitor, the Investigator may delay dosing until the parameters above are met.

If a subject fails to come to their respective study site for a scheduled study visit that includes SC administration of study drug, the investigator should contact the Gilead medical monitor to discuss if a late dose is acceptable or if the dose should be skipped.

If a subject misses 2 doses defined as the series of study drug SC injections associated with 2 study visits (clinic or home visits), the Gilead medical monitor should be contacted to discuss if the study drug should be withdrawn for that subject.

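### Protocol 5.3 withholds a dose on a pre-bronchodilator peak-flow drop with no retest, while 6.3.7 postpones only if the drop persists after a bronchodilator; the 40% FEV₁ hold is also not reconciled with eligibility at Baseline

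*Protocol*

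**What the plan says.** **Peak flow**

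- Protocol 5.3, blinded phase. One of the conditions is "AM pre-bronchodilator PEF decreases by >30% from the mean PEFR obtained during Screening during non-spirometry visits". The consequence for any listed condition is that "the subject should not be administered study drug". The investigator may delay the dose in consultation with the medical monitor. No bronchodilator retest is mentioned.
- Protocol 5.3, open-label extension. The rule is repeated as a drop of more than 30% "from the mean obtained during Screening during non-spirometry visits, or in the medical opinion of the investigator or home health provider". It does not say whether the reading is pre- or post-bronchodilator, and again gives no retest.
- Protocol 6.3.6. The third item in its hold list reads "PEF decreases by >30% from the mean obtained during Screening during non-spirometry visits, study drug dosing should be postponed". It does not say which PEF reading is meant.
- Protocol 6.3.7. On dosing days without site spirometry, a morning pre-bronchodilator PEFR is taken. If the best of three is more than 30% below the mean, "a subject may administer 2-4 puffs of a short-acting bronchodilator and repeat the PEFR 15-20 minutes later". Then: "If post-bronchodilator PEFR remains >30% below the mean PEFR value then dosing of study drug should be postponed".

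**FEV₁**

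- Protocol 5.3 also withholds when "his/her FEV₁ % predicted is less than 40" percent. It does not say pre- or post-bronchodilator, but it refers to 6.3.6 for the spirometry measures. Section 6.3.6 names the post-bronchodilator value.
- Protocol 4.2, criterion 6, requires pre-bronchodilator FEV₁ of 40% to 80% predicted at Screening. Criterion 7 requires "Two pre-bronchodilator spirometry measures taken at least 4 days apart", one at Screening and one at Baseline, differing by less than 12% and less than 200 ml.
- The first dose is given at the Baseline visit, after randomization (6.1.3). The Full Analysis Set requires at least one dose (8.2.1.1).

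**The concern.** A dose-hold rule has to give one answer for one subject on one morning. Sections 5.3 and 6.3.7 begin with the same measurement and can end differently, and 5.3 points the reader to 6.3.6, not to 6.3.7. Nothing in the text says which section governs. Some of the affected doses may be given by a home health provider, away from the study site.

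The FEV₁ hold raises a smaller matter. Eligibility and the hold both use 40% predicted, but on different readings and different days. A subject can therefore pass every entry criterion, be randomized, and meet a hold the same morning. If that subject is never dosed, a randomized subject drops out of the primary efficacy set.

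**Working it through.** The plan gives no figure of its own on this point, so the check is a comparison of the texts plus arithmetic on the protocol's limits.

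**1. The PEF rules side by side**

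| Section | Reading that decides | Retest | Result if the subject recovers after a bronchodilator |
|---|---|---|---|
| 5.3, blinded | Morning pre-bronchodilator PEF | None | Held |
| 5.3, extension | PEF, type not stated | None | Unclear |
| 6.3.6 | PEF, type not stated | None mentioned | Unclear; can be read consistently with 6.3.7 |
| 6.3.7 | Post-bronchodilator PEFR, if the first reading is more than 30% down | Allowed | Not postponed (implied) |

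Illustration with assumed values: Screening mean 400 L/min, so the limit is 0.70 × 400 = 280.

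- Pre-bronchodilator reading 270: 1 − 270/400 = 32.5% below. Section 5.3 holds the dose.
- Repeat reading 300: 1 − 300/400 = 25% below. Section 6.3.7 does not postpone.

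The relative rise needed to clear the 6.3.7 limit from a drop d is 0.70/(1 − d) − 1. That is 1.4% for d = 31%, 7.7% for d = 35% and 16.7% for d = 40%. Just beyond the limit, a very small rise is enough to make the two sections disagree.

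**2. Where it applies**

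Blinded doses fall at Baseline and Weeks 1 to 7, eight in all. The schedule (Protocol Table 6-1; SAP Appendix 1) has PEFR without spirometry at Weeks 1, 3, 5 and 7, so the PEF rule governs four of the eight. Weeks 3, 5 and 7 may be home visits (6.1.6).

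**3. Lowest eligible Baseline FEV₁**

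Take a subject at exactly 40% predicted at Screening. The permitted fall is just under the smaller of 12% and 200 ml. The 200 ml limit is the tighter one only when Screening FEV₁ exceeds 0.200/0.12 = 1.667 L. The documents give no predicted volumes; I assume a range of 2.5 to 5.5 L.

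- Predicted 2.5 L: Screening 1.000 L, fall 0.120 L, floor 0.880/2.5 = 35.2%.
- Predicted 5.5 L: Screening 2.200 L, fall 0.200 L, floor 2.000/5.5 = 36.4%.

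The highest Screening value from which Baseline can fall below 40% is the smaller of 40/0.88 = 45.5% and 40 + 20/(predicted litres). That gives 45.5% at 2.5 L and 43.6% at 5.5 L.

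**4. When such a subject meets the hold**

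Section 6.3.6 tests the post-bronchodilator value. From the floor, the subject escapes the hold only if FEV₁ rises by at least 40/35.2 − 1 = 13.6% (predicted 2.5 L) or 40/36.36 − 1 = 10.0% (predicted 5.5 L). A subject nearer 40% needs less. The repeat-spirometry allowances in 6.3.6 (38-39.9%, 80.1-82%, 12.1-14%) do not add a 40% floor at Baseline.

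**The case against.** The strongest reply is that most of this is already answered, and several parts of that reply stand.

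- A reader might infer that 6.3.6 also contradicts 6.3.7. It does not: it leaves the PEF reading unspecified, and the same sentence uses post-bronchodilator FEV₁. It is unclear, not opposed.
- A reader might infer a contradiction over which FEV₁ reading 5.3 uses. Its cross-reference to 6.3.6 largely settles that in favor of the post-bronchodilator value.
- A reader might call the 40% overlap a contradiction. It is not. Criterion 6 is an entry test at Screening, and the hold is a same-day check on a different reading. Section 5.7 foresees a subject randomized but not dosed for safety, though only in the context of rescreening after imaging.
- A reader might infer that exposure becomes tied to outcome and varies by site. The documents do not support this. A hold is first a postponement, with a window of ±3 days at later blinded dosing visits. Delay under 5.3 and two missed doses both go to the medical monitor. Any lung-function safety hold links exposure to lung function, harmonized or not.
- Nor can a hold rate be derived. The SD of 7 in the sample-size section is for change from Baseline, and the result would depend mostly on the starting value chosen.

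What the reply does not remove is 5.3 against 6.3.7. The delay in 5.3 lasts until its own conditions are met, and its condition is a pre-bronchodilator reading. A post-bronchodilator recovery does not satisfy it.

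**Conclusion.** The point holds as a wording conflict between two safety instructions. Section 5.3 withholds on the pre-bronchodilator PEF; 6.3.7, by implication and not in express words, lets dosing proceed after recovery on retest. It reaches four of the eight blinded doses. The extension text in 5.3 and item 3 of 6.3.6 leave the reading undefined.

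The secondary point holds as a possibility. An eligible subject can be randomized with a Baseline pre-bronchodilator FEV₁ as low as about 35-36% predicted (35.2% to 36.4% over the assumed predicted range). Whether the 6.3.6 hold is then met depends on bronchodilator response. Loss from the Full Analysis Set follows only if the subject is never dosed.

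No bias in the efficacy comparison is shown. The trial stopped after 6 subjects and the SAP plans no inference, so the value now lies in reading the listing of study drug administration and in any reuse of this protocol text.

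**What to change.** - Reconcile 5.3 (blinded and extension), 6.3.6 and 6.3.7 into one hold rule, stated once and cross-referenced elsewhere. It should name the PEF reading used, how many efforts are taken, and whether a post-bronchodilator retest counts.
- State in 5.3 the FEV₁ reading that 6.3.6 already specifies.
- Reconcile the FEV₁ hold with inclusion criteria 6 and 7 at Baseline, and say what happens to a subject who is randomized and then held before the first dose. The window row of the schedule appears blank at Baseline, so rescheduling within the visit window needs a meaning there.

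Which reading and which rule to adopt is the sponsor's clinical decision. The cost is protocol wording in three sections plus a reference to the entry criteria; no change to sample size or analysis is needed.
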